12.6 Follow-up of adverse events

All SAEs and MESIs must be followed up until the outcome of the event is “recovered”, “recovered with sequelae” or “fatal”, and until all queries have been resolved. Cases of chronic conditions, cancer or AEs ongoing at time of death (where death is due to another AE) may be closed with the outcome “recovering” or “not recovered”, when the subject has completed the follow up period. The follow-up period for this trial is one week (Visit 26).

The follow-up information on SAEs should only include new (corrections or new or additional) information and should be reported **within 24 hours** of obtaining knowledge of the information. This is also the case for previously non-serious AEs which subsequently become SAEs.

The follow-up information on MESIs should only include new (corrections or new or additional) information and must be reported within 14 calendar days of the investigators first knowledge of the information. This is also the case for previously reported non serious AEs which subsequently fulfil the MESI criteria.

Non-serious AEs must be followed until the outcome of the event is “recovering”, “recovered” or “recovered with sequelae” or until the end of the follow-up period stated in the protocol, whichever comes first, and until all queries related to these AEs have been resolved. Cases of chronic conditions or cancer or AEs ongoing at time of death (where death is due to another AE) may be closed with the outcome “recovering” or “not recovered”.

Queries or follow-up requests from Novo Nordisk should be responded to within 13 calendar days.

The investigator must forward follow-up information on SAEs within 24 hours and MESIs within 14 days of obtaining the follow-up information by updating the AE form in the eCRF and/or completing a new SIF marked follow-up, and forward this to Novo Nordisk. If for any reason the eCRF is unavailable or, after access to edit the eCRF is revoked, the investigator must record any SAE and MESI follow-up information on the provided paper CRFs and/or SIF and send the information by fax, e-mail or courier to Novo Nordisk.

The investigator must record follow-up information on non-serious AEs by updating the AE form in the eCRF. If the eCRF is revoked after access to edit, the investigator must record any follow-up information on the provided paper CRFs. Information on AEs, SAEs and MESIs for Visit 27 and 28 must be recorded on the provided paper CRFs.

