5.2 Rationale for trial design

A randomised double-blind design was chosen for the efficacy endpoints in order to limit the bias in the conduct and interpretation of the trial. An effect on HbA_{1c} as well as durability effects should be seen by 26 weeks²³. Stratification has been implemented in order to avoid bias arising from gender

and age at end of treatment (≤ 14 and > 14 years of age) (see section [5.1](#) for definition of ≤ 14 years of age).

Subjects' treatment allocation will be unblinded after 26 weeks in order to enable discontinuation of the liraglutide placebo injections which are considered a burden to the children and adolescents.

The current standard of care for this population is metformin treatment or insulin if needed. Subjects will, in order to ensure adequate treatment, be treated with metformin at a dose ≥ 1000 mg and ≤ 2000 mg, throughout the trial. This metformin dose is generally approved for children and adolescents. Subjects entering the trial on a dose of metformin > 2000 mg will be allowed to remain on that dose.

The 26 weeks open label extension has been added in order to assess the safety of liraglutide treatment in the paediatric population. The 2 years follow-up for subjects treated with liraglutide for more than 3 months is added in order to assess any potential long time effect on growth, pubertal development and general safety.

A rescue criterion has been implemented in order to attempt to improve retention in order to obtain additional safety information, and to mimic what would likely occur in clinical practice.

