6.8 Rationale for trial population

There is an unmet need for treatment of children and adolescents with type 2 diabetes. Metformin is the most commonly used treatment for type 2 diabetes in children and adolescents^{2,3}. However, it is also the only non-insulin treatment with regulatory approval, for use in children and adolescents. The addition of other therapies including a GLP-1 analogue has been suggested when glycaemic control is not achieved with metformin alone⁴.

Children and adolescent ages 10–17 are the target population for this trial since the mean age for diagnosis of type 2 diabetes mellitus is 13.5 years^{4,29} and the incidence of type 2 diabetes in children less than 10 years old is low²⁶.

The inclusion of subjects on basal insulin is consistent with current clinical practice. Insulin therapy is a key component in the treatment of children and adolescents with type 2 diabetes²⁵.

7 Trial schedule

It is aimed to limit the period of competitive recruitment to a minimum and a recruitment strategy will be developed in cooperation with the participating countries.

Planned date for first patient first visit (FPFV) 01-Nov-2012

Planned date for last patient last visit (LPLV) (Visit 26) 15-July 2018

Planned date for last follow-up visit (Visit 28) 15-July 2020

The end of the clinical trial is defined as LPLV (Visit 26)

Only applicable for Mexico: Mexico can recruit up to 20 subjects

All investigators will be notified immediately when the recruitment period ends, after which no further subjects will be screened and the interactive voice/web response system (IV/WRS) will be closed for further screening.

Information of the trial will be disclosed at clinicaltrials.gov and novonordisk-trials.com. According to the Novo Nordisk Code of Conduct for Clinical Trial Disclosure, it will also be disclosed according to other requirements such as those of the International Committee of Medical Journal Editors (ICMJE)³⁰, the Food and Drug Administration Amendment Act (FDAAA)³¹, European Commission Regulation for EudraCT³² and other relevant recommendations or regulations. If a patient requests to be included in the trial via the Novo Nordisk e-mail contact at these web sites, Novo Nordisk may disclose the investigator's contact details to the patient.

8 Methods and assessments

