8.7.6 Tanner staging

Pubertal status will be recorded in the CRF at Visits 7, 13, 17, 25, 27 and 28 for children-and adolescents. Pubertal development will be assessed by the Tanner staging in accordance with stages I-V³⁴. Assessment of testicular volume (by orchidometer) stages for boys will be included. The assessments must be conducted by personnel trained in pubertal assessments.

A Tanner staging assessment performed 2 weeks before Visits 7, 13, 17, 25, 27 and 28 is acceptable as Visits 7, 13, 17, 25, 27 and 28 data assessment respectively.

The Tanner staging assessment is no longer required to be performed, once the subject reaches the Tanner stage V, as judged by the investigator.

Evidence of accelerated pubertal development as judged by the investigator at Visit 1 should be recorded as concomitant illness. Acceleration of pubertal development after Visit 1 as judged by the investigator should be recorded as an AE

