12.1 Definition of adverse events

An adverse event (AE) is any untoward medical occurrence in a subject administered a product, and which does not necessarily have a causal relationship with this treatment.

An AE can therefore be any unfavourable and unintended sign (including an abnormal laboratory finding), symptom or disease temporally associated with the use of a product, whether or not considered related to the product.

Note: This includes events from the first trial related activity after the subject has signed the informed consent and until Visit 26 (for subjects treated with liraglutide for more than 3 months until Visit 28).

AEs include:

- A clinically significant worsening of a concomitant illness.
- A clinical laboratory adverse event (CLAE): A clinical laboratory abnormality which is clinically significant, i.e. an abnormality that suggests a disease and/or organ toxicity and is of a severity that requires active management. Active management includes active treatment or further investigations, for example change of medicine dose or more frequent follow-up due to the abnormality.

The following should not be reported as AEs:

- Pre-existing conditions, including those found as a result of screening procedures (pre-existing conditions should be reported as medical history or concomitant illness).
- Pre-planned procedures unless the condition for which the procedure was planned has worsened from the first trial related activity after the subject has signed the informed consent.
- Non-serious hypoglycaemia are AEs, but are reported on hypoglycaemic forms instead of on AE forms.

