12.5 Reporting of adverse events

All events meeting the definition of an AE must be collected and reported. This includes events from the first trial-related activity after the subject has signed the informed consent until the end of the post-treatment follow-up period (Visit 26). The events must be recorded in the applicable forms in a timely manner.

During each contact with the trial site staff (site visits and telephone contacts), the subject must be asked about AEs and technical complaints. This could be done by asking for example: “Have you experienced any problems since the last contact?”. Collection on technical complaints will start from the randomisation visit (Visit 7) which is the first visit where the subject will use liraglutide and the pen-injector.

At the follow-up Visits 27-28 the site will record reported AEs and SAE (based on the subject’s memory) and the associated concomitant medication. The SAE reporting must follow the timelines set for SAE reporting, please see below.

All AEs, either observed by the investigator or reported by the subject, must be reported by the investigator and evaluated. Novo Nordisk assessment of expectedness is performed according to the following reference documents:

- Novo Nordisk IMPs (liraglutide): Current version of the company core data sheet (CCDS) or any updates hereof.

The investigator should report the diagnosis, if available. If no diagnosis is available, the investigator should record each sign and symptom as an individual AE.

All AEs, SAEs and MESIs must be recorded by the investigator on the AE form in the eCRF. A separate AE form should be used for each diagnosis or sign and symptom. For each SAE a safety information form (SIF) should be completed in addition to the AE form in the eCRF. If several symptoms or diagnoses occur as part of the same clinical picture, one SIF may be used to describe all the SAEs.

The SIF will be a paper based form. The completed form will be faxed or emailed to Novo Nordisk according to the below timelines.

MESIs, regardless of seriousness, must be reported using the AE form and the SIF.

The investigator must ensure that the worst case severity and seriousness of an event is kept throughout the trial.

The reporting timelines for SAEs

- The investigator must enter the AE in the eCRF and tick the seriousness box within 24 hours of obtaining knowledge of the SAE. If the SAE is fulfilling the MESI criteria also tick the MESI box.

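### Protocol 12.6 ends its only adverse event follow-up period at Visit 26, while 12.1 runs the event period to Visit 28 for subjects on liraglutide for more than 3 months; some event outcomes may therefore be closed unresolved up to about 103 weeks early.

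*Protocol*

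**What the plan says.** Three neighbouring protocol sections give the end of the adverse event period.

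- **12.1** collects events "until Visit 26 (for subjects treated with liraglutide for more than 3 months until Visit 28".
- **12.5** first ends collection for everyone: "until the end of the post-treatment follow-up period (Visit 26". Later it says: "At the follow-up Visits 27-28 the site will record reported AEs and SAE".
- **12.6** names one period, with no exception for any group: "The follow-up period for this trial is one week (Visit 26". Its closing sentence nevertheless requires AEs, SAEs and MESIs for Visits 27 and 28 to be entered on paper CRFs.

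Section 12.6 then sets the rules for closing events:

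- SAEs and MESIs are followed to recovered, recovered with sequelae or fatal, with no date limit. As an exception, chronic conditions and cancer may be closed as recovering or not recovered once the subject has completed the follow-up period.
- Non-serious AEs are followed to outcome or "until the end of the follow-up period stated in the protocol, whichever comes first".

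Section 5.2 says that the two-year follow-up "is added in order to assess any potential long time effect on growth, pubertal development and general safety". Section 8.7.6 adds: "Acceleration of pubertal development after Visit 1 as judged by the investigator should be recorded as an AE". Accelerated puberty is not on the MESI list in 12.3.

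**The concern.** The sections set different end points for the same subjects, and the shorter one governs when a site may stop updating an event. Section 7 supports the shorter reading: "The end of the clinical trial is defined as LPLV (Visit 26".

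A site that follows 12.6 as written may close a non-serious case of accelerated puberty at Visit 26, although the child returns at one and two years. The same holds for a cancer or a chronic condition. A non-serious, non-MESI AE first reported at Visit 27 or 28 arises after the only follow-up period that 12.6 names, so that section sets no working follow-up duty for it.

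Slow events of this kind are what the extension was added to capture. Because closure is optional, two sites could also handle the same event differently, and the recorded outcomes would not be comparable.

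**Working it through.** **Inputs (protocol).** From 5.1: screening 2 weeks, run-in up to 12 weeks, and a maximum duration of 67 weeks including one week of follow-up. Treatment lasts 52 weeks. From the flow chart: Visit 26 at week 53 (±3 days), Visits 27 and 28 at weeks 104 and 156 (±14 days). From Section 7: the last Visit 26 is planned for 15 July 2018 and the last Visit 28 for 15 July 2020.

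**Reproducing the plan's own figure.** 2 + 12 + 52 + 1 = 67 weeks, as stated. The visit weeks also agree: 52 + 1 = 53, 52 + 52 = 104, 52 + 104 = 156.

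**Gap for a subject completing 52 weeks.**
- 156 − 53 = 103 weeks = 721 days; 721 / 365.25 = 1.97 years.
- With visit windows: 721 ± (3 + 14) = 704 to 738 days.
- Cross-check from the planned dates: 731 days, or 104.4 weeks.

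**Gap for early withdrawals.** Section 8.1.7 puts Visit 26 at 5 to 10 days after the early termination visit, so week 53 does not apply and 103 weeks is not a fixed figure for them.

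**What may be closed unresolved at Visit 26 under 12.6, for subjects on liraglutide for more than 3 months:**

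| Event | Closable at Visit 26? |
|---|---|
| Non-serious AE that is not a MESI, including accelerated puberty | Yes |
| Serious pubertal event | Only if a chronic condition |
| Cancer, including thyroid cancer | Yes |
| Chronic thyroid disease | Yes |
| Neoplasm or thyroid event that is neither cancer nor chronic (MESI) | No |
| Confirmed raised calcitonin (MESI) | Only if judged a chronic condition |

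Appendix D, to which the protocol refers for calcitonin, is not in the text reviewed, so any follow-up that it sets is not counted here.

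**Subjects within reach.** Protocol 17.1 plans 47 liraglutide subjects and assumes 22% withdrawal: 47 × (1 − 0.22) = 36.7, or about 37. This roughly counts subjects who could attend Visits 27 and 28. It does not count affected events, and the documents give no rate for those.

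**The case against.** A reader might infer that 12.6 stops all adverse event follow-up at Visit 26, so that tumour, thyroid and pubertal events in every liraglutide subject are abandoned two years early. The documents do not support that. All SAEs and MESIs are followed to outcome by default, and neoplasm, thyroid disease and confirmed raised calcitonin are MESIs (12.3). The exception covers only chronic conditions and cancer, and it permits closure without requiring it. The longer period applies only after more than 3 months on liraglutide.

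The remaining case for leaving the text alone has four parts.

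- **Recording continues.** Sections 12.5 and 12.6 both require events to be recorded at Visits 27 and 28. This stands: detection is not lost.
- **Growth and puberty are measured anyway.** Height, Tanner stage and bone age are scheduled at Visits 27 and 28 and are follow-up endpoints in both documents. This largely stands. It is not a full substitute for the event outcome, because Tanner staging stops at stage V and bone age stops once the epiphyses are fused.
- **The two tiers look deliberate.** The trial ends at Visit 26, the eCRF covers Visits 1 to 26 with paper forms after that, and SAP 1.2 leaves the one- and two-year follow-up out of the main database lock. This explains how the sentence may have arisen. It does not reconcile it with 12.1, which extends the event period for a named group.
- **Little reaches the analysis.** SAP 3.6.3 tabulates treatment-emergent events by outcome, but given the lock the main tables would not carry later outcomes even after a correction. This stands.

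**Conclusion.** The point holds as a conflict between operative rules in 12.1, 12.5 and 12.6. For subjects treated with liraglutide for more than 3 months, two groups of events may be closed unresolved at Visit 26: non-serious AEs, and SAEs or MESIs that are chronic conditions or cancer. For those completing 52 weeks this is about 103 weeks before the 12.1 period ends. The figure assumes visits on schedule and does not carry over to early withdrawals.

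The loss is confined to outcome updating. The number of events affected cannot be estimated from the documents, and the figure of about 37 subjects should not be read as such an estimate. Sample size, error rates, efficacy analyses and main-period safety tables are untouched. The matter still deserves correction, because the outcomes left open to early closure include those that the two-year follow-up was designed to observe.

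**What to change.** 1. In 12.6, define the follow-up period as ending at Visit 26, or at Visit 28 for subjects treated with liraglutide for more than 3 months.
2. Put the same end points in the general collection sentence of 12.5, so that it agrees with 12.1 and with its own later text.
3. Require the outcome of AEs, SAEs and MESIs still open at Visit 26 to be updated at Visits 27 and 28, on the paper CRFs already used there.

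With this change a non-serious AE first reported at Visit 27 would be within the follow-up period and could be updated at Visit 28. One first reported at Visit 28 would still sit at the boundary, as at any last visit.

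The cost is protocol wording in two sections and an outcome line on an existing form. No visit or procedure is added. The drawback is that some events stay open longer in the safety database.

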12.7 Technical complaints and technical complaint samples

A technical complaint is any communication that alleges defects on trial supplies. The technical complaint may be associated with an AE, but does not concern the AE itself.

Examples of technical complaints:

- The physical or chemical appearance of trial products (e.g. discoloration, particles or contamination)
- The packaging material (e.g., leakage, cracks, rubber membrane issues or errors in labelling text)
- Problems related to pen and needles (e.g., to the injection mechanism, needles, dose setting mechanism, push button or interface between the pen and the needle)

12.7.1 Reporting of technical complaints

All technical complaints on any of the following products liraglutide or liraglutide placebo and metformin which occur from the time of first usage of trial supplies until the time of the last usage of trial supplies must be collected and reported to Novo Nordisk.

The investigator must assess whether the technical complaint is related to any AE(s), SAE(s) and/or MESI(s).

Technical complaints must be reported on a separate technical complaint form and must be completed for each IMP (liraglutide and liraglutide placebo) Novo Nordisk provided NIMP (metformin) and for auxiliary supplies listed on the technical complaint form. If the technical complaint involves more than one batch number, a technical complaint form for each batch number must be completed.

The investigator must complete and forward the technical complaint form by fax, e-mail or courier to Novo Nordisk, within the same timelines as for reporting AEs, SAEs and MESIs as follows:

- Technical complaint assessed as related to an SAE within 24 hours of the trial site obtaining knowledge of the complaint
- All other technical complaints within 5 calendar days

The technical complaint form will be a paper based form.

12.7.2 Collection, storage and shipment of technical complaint samples

The investigator must collect the technical complaint sample and notify the monitor within 5 calendar days. The monitor must initiate the shipment to Novo Nordisk and ensure the sample is sent in accordance with local regulations and as soon as possible to Novo Nordisk complaint centre. A copy or a print of the technical complaint form should be sent with the sample.

The investigator should ensure that the technical complaint sample contains the batch number and, if available, the DUN.

If the technical complaint sample is unobtainable, the investigator must specify on the technical complaint form why it is unobtainable.

Storage and shipment of the technical complaint sample must be done in accordance with the conditions prescribed for the product (see section [9.3](#)).

12.8 Pregnancies

Female subjects must be instructed to notify the investigator immediately if they become pregnant during the trial. Treatment in pregnant trial subjects must be stopped immediately.

Only applicable to US: subjects must be instructed to notify the Investigator immediately if they or their partner become pregnant during the trial.

The investigator must report any pregnancy in subjects who received Novo Nordisk provided trial product. **Only applicable to US:** Pregnancies in partners of male subjects must be reported also (see section [12.8.1](#))

When an abnormality is reported in the foetus or newborn infant and information is needed from the male partner an informed consent must be obtained prior to this.

The investigator must report all information on pregnancies, including AEs in the subject, foetus, and newborn infant on the trial related pregnancy forms. Novo Nordisk will provide investigators with paper pregnancy forms. The pregnancy forms must be forwarded to Novo Nordisk preferably electronically in PDF format or by fax, see Attachment II.

The investigator must follow the pregnancy until the pregnancy outcome and the newborn infant(s) until the age of one month. The investigator must collect information on the pregnancy and pregnancy complications as well as the pregnancy outcome including the health of the newborn infant(s) on the pregnancy forms.

The following must be collected:

- Initial information **within 14 calendar days of the investigator's first knowledge of the pregnancy**
- Information on the outcome of her pregnancy - including the health status of the newborn infant at the age of one month **within 14 calendar days of the investigator's knowledge of the pregnancy outcome**
- All non-serious **AEs** in connection with the pregnancy and pregnancy outcome must be reported on the pregnancy forms within 14 calendar days of the investigator's knowledge. It must be clear in the description if the event occurs in the subject, the foetus or the newborn infant.

- All **SAEs** in connection with the pregnancy and pregnancy outcome must be reported on the pregnancy forms following the **same timelines as required for other SAEs** (see section [12.5](#)). It must be clear in the description if the event occurs in the subject foetus or the newborn infant.
 - The SAEs that must be reported include abnormal outcome - such as congenital anomalies, foetal death and termination of pregnancy (spontaneous or elective abortion), including any anomalies of the foetus observed at gross examination or during autopsy - as well as other pregnancy complications fulfilling the criteria of an SAE.

